4.4. Exploratory Endpoints Analyses

The exploratory analyses will be based on the ITT Analysis Set, unless otherwise specified.

4.4.1. Definition of Exploratory Endpoints

4.4.1.1. Incidence of Hospitalisation through Day 29

A participant is defined as requiring hospital stay if they received any in-patient healthcare (A&E, general ward or ICU) encounter of any duration.

Data will be summarised as collected (while-alive estimand strategy) in addition to assuming participants who die prior to Day 29 to have met the endpoint (composite estimand strategy).

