4.3.1.2. Immunogenicity of VIR-7831

The incidence and titers (if applicable) of serum ADA to VIR-7831 will be listed and summarized for the Week 36 safety summary in the Safety analysis set.

Additional immunologic analyses may be conducted and will be documented in a separate technical document.

4.3.1.3. Progression of COVID-19 by Day 29 (emergency room, hospitalisation for any duration or cause, death)

Progression of COVID-19 through Day 29 as defined by:

1. Visit to a hospital emergency room for management of illness
- OR
2. Hospitalization for acute management of illness for any duration and for any cause
- OR
3. Death

4.3.1.4. Proportion of Participants Who Progress to Develop Severe or Critical Respiratory COVID-19 at Day 8, 15, 22 and 29

Participants are defined as progressing to develop severe respiratory COVID-19 if they require supplemental oxygen either by nasal cannula, face mask, high-flow oxygen devices, or non-invasive ventilation.

Participants are defined as progression to critical respiratory COVID-19 if they require invasive mechanical ventilation or ECMO.

Participants who die prior to the timepoint of interest without first having received supplemental oxygen will be considered to have met the endpoint (composite estimand strategy).

Further detail on the severity of respiratory COVID-19 based on the proportion of participants meeting each tier of the Vir modified version of the NIAID Ordinal Scale for Clinical Improvement (Table 1) will be summarized.

Table 1 Ordinal Scale for Clinical Improvement

Ordinal Scale (Vir modified version, adapted from the Adaptive COVID-19 Treatment Trial [ACTT], 2020; referred to as National Institute of Allergy and Infectious Disease (NIAID) scale hereafter)
1) Not hospitalized, no limitations of activities
2) Not hospitalized, limitation of activities and/or requiring home oxygen ¹
3) Hospitalized, not requiring supplemental oxygen and no longer requiring ongoing medical care (used if hospitalization was extended for infection-control reasons)
4) Hospitalized, not requiring supplemental oxygen but requiring ongoing medical care (COVID-19-related or other medical conditions)
5) Hospitalized, requiring any supplemental oxygen
6) Hospitalized, requiring non-invasive ventilation or use of high-flow oxygen devices
7) Hospitalized, receiving invasive mechanical ventilation or ECMO ²
8) Death

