4.4.2. Main Analytical Approach

All exploratory endpoints will be summarised only.

Total hospital length and total intensive care length of stay will only be summarised if at least 10% of participants have one or more recorded event of interest. Length of stay will be summarised in all patients in the analysis set, in addition to those with the event of interest. Otherwise the data will be listed only.

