5. SAMPLE SIZE DETERMINATION

Sotrovimab IM participants and sotrovimab IV participants were planned to be enrolled and randomized in a 1:1:1 ratio to receive a single dose IV infusion of sotrovimab or a single IM injection of sotrovimab at one of two dose levels, in an open-label manner.

Approximately 1020 (340 per arm) participants were planned to be randomly assigned to study intervention. This sample size will provide approximately 90% power to demonstrate that IM

injection of sotrovimab is non-inferior to IV infusion of sotrovimab in terms of the proportion of participants with progression of COVID-19 through Day 29 at the one-sided 2.5% significance level assuming COVID-19 progression rates of 2% in the sotrovimab IM and IV arms and 3.5% non-inferiority margin on the risk difference scale.

Following the discontinuation of sotrovimab 250 mg IM arm (See Section 4.7), no more participants were enrolled and randomized into this arm. The remaining participants were randomized in a 1:1 ratio to receive sotrovimab 500mg IV or sotrovimab 500 mg IM

Sample Size/Power Sensitivity

The table below shows power for showing non-inferiority for different true progression rates on the sotrovimab IV arm and when the progression rate in the sotrovimab 500mg IM arm is equal to or higher than that on IV, given a sample size of N=340 per arm.

		Progression rate in sotrovimab IV arm		
		1.0%	1.5%	2.0%
Progression rate in sotrovimab IM arm minus Progression rate in sotrovimab IV arm	0% (equal)	>99%	96%	90%
	+0.1%	99%	95%	88%
	+0.2%	98%	93%	85%
	+0.3%	97%	91%	82%

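### The exploratory definition of hospital stay can take in A&E attendances, and the 10% rule for summarising length of stay is effectively out of reach for ICU stay and unlikely to be met for hospital stay

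*SAP*

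**What the plan says.** SAP 4.4.1.1 (incidence) and 4.4.1.2 (total hospital length of stay) share one definition: "A participant is defined as requiring hospital stay if they received any in-patient healthcare (A&E, general ward or ICU) encounter of any duration". Incidence is reported in two versions, one as collected while alive and one that counts death before Day 29 as an event. SAP 4.4.1.4 defines intensive care by an ICU encounter only, so A&E does not enter there.

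The secondary progression endpoint (SAP 4.3.1.3) has three separate components. The first is "Visit to a hospital emergency room for management of illness"; the others are hospitalisation of any duration for acute illness, and death.

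SAP 4.4.2 states that total hospital and ICU length of stay "will only be summarised if at least 10% of participants have one or more recorded event of interest". Below that level the data are listed. Above it, they are summarised both for everyone in the analysis set and for those with the event. The SAP does not say whether the 10% applies per arm or overall.

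SAP 1.1 gives the exploratory objective, which includes describing the duration of hospital and ICU stay for IM versus IV. SAP 5 sizes the trial "assuming COVID-19 progression rates of 2% in the sotrovimab IM and IV arms", where progression means hospitalisation over 24 hours or death (SAP 4.2.1).

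**The concern.** There are two problems, and they interact.

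First, the SAP separates emergency room visits from hospitalisation in the secondary endpoint but puts A&E inside hospital stay in the exploratory ones. If A&E attendances without admission are counted, the incidence of hospitalisation mixes two kinds of event, and short A&E visits also enter total length of stay. On that reading the version that counts deaths comes close to the secondary endpoint, and no endpoint in the SAP isolates the cumulative incidence of admission of any duration.

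Second, the length-of-stay tables depend on an event frequency far above the planning rate. If the threshold is missed, the duration part of the objective has no summary by arm. Whether it is missed for hospital stay depends partly on the unsettled A&E question.

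**Working it through.** **Inputs.** From SAP 5: "Approximately 1020 (340 per arm) participants were planned to be randomly assigned to study intervention", so 680 in the two 500 mg arms; 2% progression in both arms; margin 3.5%; one-sided 2.5%; power about 90%. From SAP 4.4.2: threshold 10%. From Protocol 1.1: observed Day 29 primary rates of 2.7% (500 mg IM) and 1.3% (500 mg IV).

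**The plan's own figure.** With an unpooled normal approximation, power at 340 per arm is Φ(0.035 / √(2 × 0.02 × 0.98 / 340) − 1.96) = Φ(0.035 / 0.01074 − 1.96) = Φ(1.30) = 90.3%. The size needed for 90% is 337 per arm, against 340 stated. The same formula matches all 12 cells of the SAP power table, so 2% and 340 are read correctly.

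**Events needed and expected.** In 680 participants the threshold is 0.10 × 680 = 68. At 2%, 0.02 × 680 = 13.6 are expected. The observed primary rates give the same total if each arm had 340: 0.027 × 340 + 0.013 × 340 = 9.2 + 4.4 = 13.6.

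**Probability of reaching the threshold.** Exact binomial tail, P(X ≥ 0.10 N) with X ~ Bin(N, p). Three denominators are shown because the SAP does not fix one: a single arm, the two 500 mg arms, and all three planned arms.

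| True event rate | N = 340 (34 needed) | N = 680 (68 needed) | N = 1020 (102 needed) |
|---|---|---|---|
| 2% | 3e-14 | 8e-27 | 2e-39 |
| 4% | 1e-6 | 1e-11 | 9e-17 |
| 6% | 0.3% | 3e-5 | 5e-7 |
| 8% | 11% | 3.5% | 1.3% |
| 9% | 29% | 20% | 14% |
| 10% | 53% | 52% | 52% |

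**Which row applies.**
- *ICU stay.* A&E does not count. I assume that the ICU rate would rarely exceed the rate of hospitalisation over 24 hours or death. The 2% row is then close to an upper case, and the threshold is effectively unreachable.
- *Hospital stay.* The event is wider than the primary endpoint, and the documents give no rate for it. The rows from 2% to 10% are an assumed range. Starting from about 14 primary events, roughly 68 − 14 = 54 further participants with short or A&E-only encounters would be needed. An even chance of a summary needs a true rate of about 10%, five times the planning rate.

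**The case against.** **The word in-patient governs the list.** A&E can be read as a place of admission, and the SAE definition in Protocol 10.3.2 likewise treats admission to an emergency ward as hospitalisation. On that reading the exploratory incidence is admissions of any duration. This stands as far as it goes: the wording is ambiguous rather than plainly wrong. The ambiguity still changes both the incidence and the length of stay, and the SAP does not settle it.

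**The exploratory endpoint does not repeat the secondary one.** A reader might infer that it does; the documents do not support that. Only the version that counts deaths comes close, and only if A&E visits without admission count. The while-alive version leaves death out. The exploratory definition has no restriction to management of illness. It is summarised as collected, whereas the secondary endpoint is modelled with multiple imputation (SAP 4.3.2.1 and 6.2.8). Study day runs from randomisation for hospitalisation incidence and duration, and from treatment start for progression (SAP 6.2.4).

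**The 2% belongs to a narrower event.** It is also tempting to conclude from it that neither length-of-stay table will be produced. That is not shown for hospital stay, because the A&E-inclusive rate is unknown; the table is unlikely, not ruled out. For ICU stay the inference is much stronger.

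**The data are not lost.** Individual stays are still listed. Incidence of hospitalisation and the proportion with ICU stay or ventilation fall outside the 10% rule, and the ordinal scale in SAP 4.3.1.4 shows hospitalised status. So it would be wrong to say that the whole objective cannot be answered; what is at risk is the summary of duration by arm. Listing about 14 stays is a defensible choice for an exploratory endpoint, but a listing does not give the description by arm that the objective asks for. Displays are detailed in a separate specification that is not public, so a further table separating admissions cannot be excluded.

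**Conclusion.** The point holds as a low-cost improvement. The definition allows A&E attendances to be counted as hospitalisation, against the separation made in the secondary endpoint, and it needs clarifying. The 10% condition makes the ICU length-of-stay summary effectively unreachable (about 8e-27 at 2% in 680) and the hospital summary unlikely unless the true rate nears 10% (3e-5 at 6%, 3.5% at 8%, 20% at 9%, 52% at 10%). The description of duration by arm would then very probably rest on a listing alone.

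This rests on three assumptions: ICU stay is no more common than the primary endpoint; the A&E-inclusive rate lies within the range shown; and the 10% is judged over the two 500 mg arms. Judging it in a single arm or over all three planned arms does not change the conclusion for ICU stay. In a single arm, the chance of a hospital summary at 8% rises to 11%.

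The effect is small. These are descriptive, exploratory endpoints of the IM/IV study, no primary conclusion depends on them, and the Amendment 4 safety substudy has no length-of-stay endpoint.

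**What to change.** 1. In SAP 4.4.1.1 and 4.4.1.2, define hospital stay as admission to a ward or ICU, and report A&E-only encounters in a separate row.
2. In SAP 4.4.2, drop the 10% condition. Always give hospital days and ICU days per participant by arm, with zero for those not admitted, alongside the listing of individual stays. The question of whether 10% is per arm or overall then disappears.
3. Record the change as made after the Day 29 analysis, whose results the current protocol already reports.

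The cost is SAP wording and two small tables from encounter and duration data that these endpoints already require. The drawback is that the tables will be sparse.

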4.4.1.2. Total Hospital Length of Stay

A participant is defined as requiring hospital stay if they received any in-patient healthcare (A&E, general ward or ICU) encounter of any duration. A participant may have more than one period of hospital stay included in the total hospital length of stay.

Data will be summarised as collected (while-alive estimand strategy) in addition to assuming participants who die prior to Day 29 to have been in hospital from the date of death to Day 29 (composite estimand strategy).

4.4.1.3. Proportion of subjects requiring ICU stay or mechanical ventilation through Day 29

A participant is defined as being on a ventilator if they received invasive mechanical ventilation or ECMO as a form of oxygen therapy. A participant is defined as requiring intensive care if they received an intensive care unit in-patient healthcare encounter of any duration.

Data will be summarised as collected (while-alive estimand strategy) in addition to assuming participants who die prior to Day 29 to have met the endpoint (composite estimand strategy).

4.4.1.4. Total Intensive Care Length of Stay

A participant is defined as requiring intensive care if they received an intensive care unit in-patient healthcare encounter of any duration. A participant may have more than one period of intensive care stays included in the total intensive care length of stay.

Data will be summarised as collected (treatment policy estimand strategy) in addition to assuming participants who die prior to Day 29 to have been in intensive care from the date of death to Day 29 (composite estimand strategy).

4.4.1.5. SARS-CoV-2 Resistant Mutants Against VIR-7831 at Baseline

Summaries of viral resistance mutations at baseline will be provided based on frequency counts in the Safety analysis set.

4.4.1.6. Emergence of SARS-CoV-2 Resistant Mutants Against VIR-7831

Summaries of viral resistance mutations will be provided based on frequency counts in the Safety analysis set.

4.4.1.7. Reduction in SARS-CoV-2 Viral Load

Viral load will be \log_{10} -transformed prior to summary and analysis. The Virology analysis set will be used for all analyses.

Reduction of SARS-CoV-2 viral shedding will be determined by the change from baseline of SARS-CoV-2 nasal viral load at Day 3, Day 5, Day 11, Day 15, Day 22, and Day 29.

In addition, the SARS-CoV-2 viral load will also be assessed from the area under the curve (AUC as determined by the trapezoidal rule) of \log_{10} -transformed SARS-CoV-2 viral load through Days 1 to 5 (AUC_{D1-5}) and Days 1 to 11 (AUC_{D1-11}). AUC will be log-transformed prior to analysis.

The proportion of participants with undetectable, unquantifiable and positive SARS-CoV-2 in nasal secretions by qRT-PCR at Day 3, Day 5, Day 8, Day 11, Day 15, Day 22, and Day 29 will be summarised.

In addition a Kaplan-Meier plot of time to undetectable SARS-CoV-2 in nasal secretions by qRT-PCR by treatment group will be produced. For the purposes on the plot, a confirmed negative PCR is defined as first of two or more consecutive negative (no SARS-CoV2 detected) PCR tests.

4.4.1.8. SARS-CoV-2 viral load measured by qRT-PCR

Summaries will be provided to compare different sample collection methods in SARS-CoV-2 viral load (e.g. nasopharyngeal swab, saliva) within participants. The Virology analysis set will be used for all analyses.

4.4.1.9. SARS-CoV-2 anti-N antibody at Day 1 and Day 29

The incidence and titers (if applicable) of anti-N SARS CoV-2 antibodies at Day 1 and Day 29 will be summarized using frequency counts by treatment (including a total column) in the Safety analysis set.

4.4.1.10. Incidence and severity of Long COVID symptoms at Week 12, Week 24 and Week 36

To monitor for subsequent development of long COVID at Week 12, Week 24 and Week 36, participants will be asked a series of questions to evaluate a range of symptoms after first being infected with the SARS-CoV-2. The questions to be asked are defined in Appendix 6 of the Protocol.

The participant responses to the questions will be summarised, based on ITT analysis set. The frequency of the response Grade categories (“Grade 1” to “Grade 3”) will be presented for each question.

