Pharmacokinetics 
 Assess the pharmacokinetics (PK) of sotrovimab in serum following IV and IM (two dose levels) administration 	
 IV and IM sotrovimab pharmacokinetics (PK) in serum
Exploratory	

 Describe the effect of two doses levels of intramuscular versus intravenous sotrovimab on incidence and duration of time on total hospital length of stay (LOS), incidence and duration of time on a ventilator, and ICU length of stay 	
 Incidence of hospitalization through Day 29 Total hospital LOS Proportion of participants requiring ICU stay or mechanical ventilation through Day 29 Total ICU LOS

 Monitor SARS-CoV-2 resistant mutants against sotrovimab 	
 SARS-CoV-2 resistance mutants to sotrovimab at baseline Emergence of viral resistance mutants to mAb by SARS-CoV-2

 Compare the virologic activity of sotrovimab given IM (two dose levels) or IV in reducing SARS-CoV-2 viral load 	
 Change from baseline in viral load in nasal secretions by qRT-PCR during follow-up period at Day 5, Day 11, Day 15, Day 22 and Day 29

Objectives	Endpoints
	
 Undetectable SARS-CoV-2 in nasal secretions by qRT-PCR at Day 3, Day 5, Day 8, Day 11, Day 15, Day 22 and Day 29 Mean area under the curve of SARS-CoV-2 viral load as measured by qRT-PCR from Day 1 to Day 5 (AUC_{D1-5}) and Day 1 to 11 (AUC_{D1-11})

 Compare the effect of different sample collection methods in SARS-CoV-2 viral load (e.g. nasopharyngeal swab, saliva) 	
 SARS-CoV-2 viral load measured by qRT-PCR

 Evaluate the effect of sotrovimab on the development of SARS-CoV-2 antibodies 	
 SARS-CoV-2 anti-N antibody at Day 1 and Day 29

 Describe the effect of sotrovimab on Long COVID symptoms 	
 Incidence and severity of Long COVID symptoms at Week 12, Week 24 and Week 36

Primary estimand

The primary efficacy endpoint will primarily be assessed using an estimand that uses a hypothetical strategy to deal with the main intercurrent events. The estimand is described by the following attributes:

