3. ANALYSIS SETS

Analysis Set	Definition / Criteria	Analyses Evaluated
Screened	All participants who were screened for eligibility	Study Population
Enrolled	All participants who entered the study Note screening failures (who never passed screening even if rescreened) are excluded from the Enrolled analysis set as they did not enter the study	Study Population
Randomized	All participants who were randomized. Participants will be analyzed according to the route of administration and dose level they were randomized to: sotrovimab IM (500 mg), sotrovimab IM (250 mg) or sotrovimab IV (500 mg).	Study Population
Intent-to-Treat (ITT)	All participants who were randomized. Participants who were randomized under Protocol Amendment Version 1 and were immunocompetent and fully vaccinated at randomisation will be excluded. Participants will be analyzed according to the route of administration and dose level they were randomized to: sotrovimab IM (500 mg), sotrovimab IM (250 mg) or sotrovimab IV (500 mg).	Study Population Efficacy
Safety	All randomized participants who are exposed to study intervention. Participants will be analyzed according to the route of administration and dose level they actually received: sotrovimab IM (500 mg), sotrovimab IM (250 mg) or sotrovimab IV (500 mg).	Study Population Safety
Pharmacokinetic (PK)	All participants in the Safety analysis set who had at least 1 non-missing PK assessment (Non-quantifiable [NQ] values will be considered as non-missing values). Participants will be analyzed according to the route of administration and dose level they actually received.	PK

Analysis Set	Definition / Criteria	Analyses Evaluated
Virology	
All participants in the ITT analysis set with a lab confirmed quantifiable baseline nasopharyngeal swab at Day 1.
 
Participants will be analyzed according to the route of administration and dose level they were randomized to: sotrovimab IM (500 mg), sotrovimab IM (250 mg) or sotrovimab IV (500 mg).
 
This will be the primary analysis set for virology.
	Efficacy (Virology)

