4.1.3. Missing Data Handling Rules

- Missing data can occur due to study withdrawal or participants lost to follow-up before the completion of the study or due to intermittent missing values (i.e. data between two non-missing assessments).
- In addition, for the hypothetical estimands of the primary and secondary COVID-19 progression endpoints, data collected after the occurrence of an intercurrent event will be excluded from the analysis and will therefore be set to missing.
- For the primary and secondary COVID-19 progression endpoints, missing data will be imputed under a missing at random (MAR) assumption using a multiple imputation (MI) model. More details are provided in Section 6.2.8.

- For all other endpoints, a treatment policy strategy will be used for all intercurrent events where all data captured will be included in the summary and analysis, unless otherwise stated.

The following rules will be applied to viral load endpoints:

- The imputation logic when a sample is reported as 'NEG' (below lower-limit of detection) or '<2.08' (below lower-limit of quantification) is to impute as $0.5 \times 120 \text{ copies/ml} = 60 \text{ copies/ml} = 1.78 \log_{10} \text{ copies/ml}$
- Subjects who die prior to Day 8 (or Day 5 or Day 11), their AUC viral load value will be imputed using the worst AUC viral load value from other subjects in the same treatment arm who have completed Day 8 (5/11) and have a valid AUC(D1-8)/(D1-5)/(D1-11).
- If Day 8 assessment alone is missing but Day 5 and Day 11 assessments are available, the Day 8 will be imputed using linear interpolation between Day 5 and Day 11. AUC will be calculated then.
- If more than 2 consecutive assessments are missing prior to and including Day X, then the AUC(D1-X) will not be calculated.
- If a subject is lost to follow-up prior to Day X, then AUC(D1-X) will be set to missing.

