4.2.2.1. Key Inclusion/Exclusion Criteria

Type	Category	Criteria
Inclusion	5.1.2. Type of Participant and Disease Characteristics	
1. Participants who have a positive SARS-CoV-2 test result within 7 days of randomization (by any validated diagnostic test e.g. RT-PCR, antigen based testing on any specimen type)
 
4. Participant to be dosed less than or equal to 7 days from onset of symptoms to dosing day (D1) Note: Participants will only be excluded if ≥ 9 days since dosing.

Exclusion	5.2.1. Medical Conditions	
1. Currently hospitalized or judged by the investigator as likely to require hospitalization in the next 24 hours Note: Participants will only be excluded if hospitalized at baseline per eCRF form.

	5.2.2. Prior/Concurrent Clinical Study Experience	
5. Enrollment in any investigational vaccine study within the last 180 days or any other investigational drug study within 30 days prior to Day 1 or within 5 half-lives of the investigational compound, whichever is longer

		6. Enrollment in any trial of an investigational drug, vaccine or device study for SARS-CoV-2/COVID-19 within 90 days prior to Day 1 or within 5 half-lives of the investigational compound, whichever is longer
5.2.3. Other Exclusions		7. Immunocompetent individuals who are fully vaccinated against SARS-CoV-2. A person is considered fully vaccinated if at least 14 days have passed since receiving the final dose in a COVID-19 vaccine series. 8. Receipt of convalescent plasma from a recovered COVID-19 patient or anti-SARS-CoV-2 mAb within the last 3 months.

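### The swab–saliva viral load comparison in SAP 4.4.1.8 uses a set selected on a quantifiable Day 1 nasopharyngeal swab, which tilts the Day 1 contrast towards the swab (minor)

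*SAP*

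**What the plan says.** SAP Section 1.1 lists, as an exploratory objective, a comparison of sample collection methods, with SARS-CoV-2 viral load by qRT-PCR as the endpoint. Section 4.4.1.8 carries it out: "Summaries will be provided to compare different sample collection methods in SARS-CoV-2 viral load (e.g. nasopharyngeal swab, saliva) within participants". The population follows at once: "The Virology analysis set will be used for all analyses".

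Section 3 defines that set as "All participants in the ITT analysis set with a lab confirmed quantifiable baseline nasopharyngeal swab at Day 1". No other set or sensitivity analysis is given for this comparison.

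Three further provisions matter:

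- Section 4.1.3 sets any sample "reported as 'NEG' (below lower-limit of detection) or '<2.08' (below lower-limit of quantification" to half of 120 copies/mL, that is 60 copies/mL or 1.78 log10.
- Section 4.2.2.1 repeats the entry test: a positive result "by any validated diagnostic test e.g. RT-PCR, antigen based testing on any specimen type". Trial entry therefore does not guarantee a quantifiable Day 1 swab.
- Section 4.4.2 limits the analysis: "All exploratory endpoints will be summarised only".

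**The concern.** When two measurement methods are compared within participants, the sample should not be chosen on the result of one of them. Here, participants quantifiable by swab but not by saliva stay in, and those quantifiable by saliva but not by swab are taken out. The swab distribution is cut off from below at the limit of quantification and the saliva distribution is not. Two equally good methods would then appear to differ on Day 1, with the swab ahead.

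The Virology set makes sense for change from baseline and for treatment comparisons, where a measurable starting value is needed. That reason does not carry over to a comparison of methods, and Section 4.4.1.8 gives no other. What is at stake is the answer to one exploratory objective, for which this summary is the only planned evidence.

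**Working it through.** **Inputs from the SAP.** Limit of quantification 120 copies/mL; substituted value 60 copies/mL (Section 4.1.3). Check: log10(120) = 2.08 and log10(60) = 1.78, as stated. The SAP gives no size for the swab–saliva contrast, so there is no plan figure to reproduce.

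**Assumed inputs, not in the documents.** Swab and saliva truly equal; log10 viral load normal with mean 4.5 to 6.0 and SD 2; within-person correlation 0.4 to 0.8.

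**Step 1: mechanism, with no distributional assumption.** Let a, b and c be the shares quantifiable by both methods, by swab only and by saliva only.

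- All pairs: swab minus saliva = (a + b) − (a + c) = b − c.
- Virology set: swab = 1, saliva = a/(a + b), gap = b/(a + b).

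Since a + b ≤ 1, b/(a + b) ≥ b ≥ b − c. Selection can only move this contrast towards the swab or leave it unchanged. Example with equal true rates of 90% and correlation 0.6: saliva in the set is 93.2%, so a = 0.932 × 0.900 = 0.839, b = 0.061 and c = 0.061. The true gap is 0; the gap in the set is 0.061/0.900 = 6.8 percentage points.

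**Step 2: mean viral load, the planned endpoint.** The swab mean in the selected set is that of a truncated normal:

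μ + σ·φ(k)/Φ(k), with k = (μ − 2.08)/σ.

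- μ = 4.5: k = 1.21, Φ(k) = 0.887, φ(k) = 0.192; mean = 4.5 + 2 × 0.192/0.887 = 4.93.
- μ = 6.0: k = 1.96, Φ(k) = 0.975, φ(k) = 0.0584; mean = 6.0 + 2 × 0.0584/0.975 = 6.12.

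Without selection, both methods have mean 0.887 × 4.93 + 0.113 × 1.78 = 4.58, or 0.975 × 6.12 + 0.025 × 1.78 = 6.01. Saliva in the selected set was obtained from simulated bivariate-normal pairs, with values below the limit set to 1.78:

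| Mean | Correlation | Swab mean in set | Saliva mean in set | False swab advantage | Saliva quantifiable in set (true rate) | Saliva-only share dropped* |
|---|---|---|---|---|---|---|
| 4.5 | 0.4 | 4.93 | 4.73 | 0.20 | 90.9% (88.7%) | 8.4% |
| 4.5 | 0.8 | 4.93 | 4.86 | 0.07 | 94.6% (88.7%) | 5.1% |
| 6.0 | 0.4 | 6.12 | 6.06 | 0.06 | 97.8% (97.5%) | 2.2% |
| 6.0 | 0.8 | 6.12 | 6.10 | 0.02 | 98.6% (97.5%) | 1.4% |

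*Of those quantifiable by either method.

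Selection raises both means, but the swab's by more: at mean 4.5 and correlation 0.4, the swab goes from 4.58 to 4.93 and saliva from 4.58 to 4.73. The direction requires that saliva regress on swab with a slope below 1, which holds for equal methods with imperfect correlation.

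**Step 3: sensitivity.** If only 80% were quantifiable by each method (mean 2.08 + 2 × 0.84 = 3.76), the false advantage would be 0.31 log10 at correlation 0.4 and about 0.11 at 0.8.

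**Step 4: other sets.** Under the same assumptions, the mean difference is about 0 in all pairs and also about 0 in pairs quantifiable by either method. Either choice removes the built-in advantage.

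**The case against.** The strongest case for leaving the plan alone is that little depends on it. The endpoint is exploratory and only summarised, with no hypothesis or decision rule. The false difference is small beside the rise of more than 1 log10 that Protocol Section 8.3.5 uses to define virologic rebound, and every input to its size is assumed. The documents do not show when saliva was taken: SAP version 2.0 rests on Protocol Amendment 3, while the available Amendment 4 schedule covers the safety substudy and lists only nasopharyngeal swabs. If there was no Day 1 saliva sample, the forced cut-off does not apply directly. All of this stands and limits the severity. It does not remove the bias from the stated rule, and descriptive status does not make a tilted contrast informative.

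Two stronger readings are tempting. A reader might infer that saliva is made to look worse than it really is. That is not so: with positively correlated methods, saliva's own figures rise in the selected set (for example from 88.7% to 90.9% quantifiable), and only the contrast with the swab is distorted. A reader might also infer that a planned Day 1 detection or agreement result is spoiled, because the swab is quantifiable in 100% by definition. Section 4.4.1.8 plans viral load summaries and names no such table. The detection categories in Section 4.4.1.7 are for nasal secretions from Day 3 on.

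**Conclusion.** The point holds as a minor one. Taken as written, Sections 3 and 4.4.1.8 tilt the Day 1 swab–saliva contrast in viral load towards the swab. The direction follows from the set definition plus imperfect correlation between comparable methods. The size, about 0.02 to 0.20 log10 copies/mL, rests wholly on the assumptions of equal methods, mean 4.5 to 6.0 log10, SD 2 and correlation 0.4 to 0.8; it grows if fewer participants are quantifiable. The cut-off acts on Day 1. At later visits the selection works only through correlation with the Day 1 swab and should matter less; that was not quantified. The point concerns the IM/IV study covered by the SAP, and no primary, secondary or safety conclusion changes.

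**What to change.** In Section 4.4.1.8 only, replace the Virology set with all participants who have same-visit samples by each of the methods compared, regardless of the nasopharyngeal result, and summarise the paired difference by visit. Participants quantifiable by either method can serve as an alternative or sensitivity set. A paired table of quantifiable against non-quantifiable results would be a useful optional addition. Keep the Virology set for the treatment comparisons.

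The cost is a short change of text and a little extra descriptive output, limited to visits where paired samples exist; the documents do not show which visits those are. Pairs non-quantifiable by both methods enter as 1.78 against 1.78, add no information and pull the mean difference towards zero, which is the reason to show the either-method set as well. The protocol already reports Day 29 results, so if this summary has been produced, the revised one should be labelled as added after the fact, and the existing one should state that its set was selected on the swab.
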